All patients of the R-only group received the laser treatment after the termination of the CoRaLa I study (after month 12). However, this late treatment did not seem to improve the final results. It could be speculated, that the timing of the laser photocoagulation might be an important factor influencing the effect of this additional treatment. Hypothesis that only early laser photocoagulation improves the final results of the anti-VEGF treatment in CRVO patients may be supported by observations of Spaide [22], who evaluated the effect of non-selective laser treatment of peripheral retinal non-perfusion after the initial six monthly Ranibizumab injections were given prior to enrolment into the study (N=22).

The study showed a weak descriptive decrease of BCVA from 54.2(± 10.7) to 51.4(± 18.8) ETDRS ([means (SD)]; although accompanied by relevant heterogeneity) and no significant difference in the number of Ranibizumab injection during 6 months before and after the photocoagulation (3.4 vs. 3.1 injections). However, 17 of 22 patients in the study had a history of previous intravitreal steroids or of anti-VEGF injections [22].

In the CoRaLa I study we enrolled treatment-naïve patients in whom an early selective photocoagulation of peripheral areas of nonperfusion was performed. Recently, further studies described results which are in line with the observations of the CoRaLa I [20,21]. In prospective non-randomized trial Tultseva et al. [20] showed a significantly smaller number of required Ranibizumab injections in CRVO patients treated additionally with scatter laser photocoagulation of peripheral ischemic retina during 24-28 months of trial duration when compared to control group treated with Ranibizumab only [3.5(± 1.6) vs 10.6(± 2.5) Ranibizumab injections respectively].

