9.5.2 Planned Methods for Analysis

Analysis of the *primary endpoint* (within the FAS, [31]) will follow the intent-to treat principle and will be based on COX regression with the stratification factor baseline BCVA (≤ 55 letters vs > 55 letters) as fixed covariate for confirmatory analysis.

Further models will include potentially prognostic factors and compliance for sensitivity reasons. The assumption of proportional hazard may be justified although no similar data are available by now. It will be checked and otherwise adequately dealt with. Kaplan-Meier curves provide time without treatment success per arm.

The *number of Ranibizumab injections* required after the initial three injections will be analysed by an ANCOVA *model* including treatment as factor and baseline BCVA as covariate (also used for stratification); for sensitivity reasons, further models may include the same prognostic factors of potential relevance as selected for analyses of the primary endpoint.

To adequately analyse the long-term *courses of BCVA and CST* at the end of study we require that patients with early treatment success have further mandatory visits beyond success since - based on CoRaLa I data - we expect rather different event times with regard to the chosen primary endpoint. Given the 6 monthly visits to determine "success", we assume that this will lead to only few additional visits per patient

In each patient, BCVA and CST will be analysed at 6 time points: at baseline visit, and after 12, 16, 20, 24 and 29 months. Analyses of both secondary endpoints are identically structured: mean changes from baseline mean will be analysed using a repeated measurement linear mixed model without intercept containing the fixed, categorical effects of

- visit (as named),
- treatment (RL vs R-only),
- treatment by visit interaction,
- low BCVA pre-treatment value (yes / no) as well as
- a patient-specific, visit random effect.

An unstructured (co-)variance structure will be used to model the residual within-patient errors. If this analysis fails (does not converge), a compound symmetry structure corresponding to a constant correlation will be used. The analysis will be based on restricted maximum likelihood

(REML). The contrast of interest is the treatment by visit interaction at 29 months. Respective inference will be based on Wald type confidence intervals and respective p-values.

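### The BCVA/CST mixed model carries a redundant visit random effect, and its only fallback, compound symmetry with model-based Wald inference, can misstate the month-29 standard error

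*Protocol*

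**What the plan says.** Section 9.5.2 analyses BCVA and CST "at baseline visit, and after 12, 16, 20, 24 and 29 months", which makes six time points. It states that "mean changes from baseline mean will be analysed using a repeated measurement linear mixed model without intercept". The listed terms are visit, treatment, their interaction, a low-BCVA indicator and "a patient-specific, visit random effect".

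A separate sentence then adds: "An unstructured (co-)variance structure will be used to model the residual within-patient errors". If that fit fails, "If this analysis fails (does not converge), a compound symmetry structure corresponding to a constant correlation will be used". Estimation is by REML.

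On the result to be reported: "The contrast of interest is the treatment by visit interaction at 29 months", and "Respective inference will be based on Wald type confidence intervals and respective p-values". The section names no reference visit for the interaction, no intermediate covariance structure and no robust variance. It does not say whether the random effect stays in the model under the fallback.

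**The concern.** There are two linked problems.

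**The model as written has more covariance parameters than the data can distinguish.** An unstructured residual matrix over six visits leaves nothing for a patient-level random effect to explain. The likelihood is flat along that direction, and software often reports this as a convergence or Hessian failure. Failure to converge is exactly the condition that moves the analysis to the fallback.

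**The fallback drops from 21 covariance parameters to 2.** The design gives reasons to doubt equal variances and equal correlations once baseline is included:
- Baseline BCVA is limited by inclusion criterion 4 to 24-78 letters; later values are not limited.
- Baseline CST is untreated oedema above 250 µm (inclusion criterion 1); later CST follows criteria-driven injections (section 6.3).
- Baseline lies about a year before the next modelled visit, whereas the later visits are 4 to 5 months apart.

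At stake are the confidence intervals and p-values of the month-29 contrast for two of the three secondary endpoints. The protocol already fixes both the model and the fallback, so this is not a detail left open for the SAP.

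**Working it through.** **1. Redundancy.** The marginal covariance for one patient is V = ZGZ' + R. With six visits V has 6×7/2 = 21 free elements. Counting parameters against the rank of the derivatives of V:

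| Specification | Parameters | Rank |
|---|---|---|
| Unstructured R alone | 21 | 21 |
| + random intercept | 22 | 21 |
| + visit effect, separate variances | 27 | 21 |
| + visit effect, unstructured | 42 | 21 |
| Compound symmetry alone | 2 | 2 |
| Compound symmetry + random intercept | 3 | 2 |

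Every random effect added to the unstructured R is redundant. V and the fixed effects remain identified.

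If the response were each patient's own change from baseline, the baseline record would be zero for everyone and a 6x6 unstructured matrix would also be singular.

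**2. Fallback, month 29 minus baseline.** With complete balanced data, REML compound symmetry estimates the mean diagonal element (s) and the mean off-diagonal element (c) of the true matrix. Per-patient contrast variances:
- compound symmetry: 2(s − c)
- true: Vb + V29 − 2·cov(b,29)
- r = √(true / compound symmetry); type I error = 2[1 − Φ(1.96/r)]. The sample size cancels in r.

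The fallback is taken to have a compound-symmetric marginal covariance, as it does if the random effect is dropped or is only an intercept.

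The protocol gives no visit SDs or correlations for this population, so the inputs are assumptions. The BCVA SDs 10.7 (baseline) and 18.8 (later) are borrowed from the external cohort described in section 1.1 ("The study showed a weak descriptive decrease of BCVA from" introduces its figures). The CST SDs (150 and 80 µm) and all correlations are assumed outright.

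*BCVA*, correlation 0.4 baseline-later and 0.8 later-later:
- s = (114.49 + 5×353.44)/6 = 313.62
- c = (5×80.46 + 10×282.75)/15 = 215.32
- compound symmetry 2(313.62 − 215.32) = 196.6; true 114.49 + 353.44 − 160.93 = 307.0
- r = √(307.0/196.6) = 1.25; type I error **11.7%**

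The grid runs over baseline-later 0.2 to 0.6 and later-later 0.6 to 0.9:
- 0.6/0.6: √(226.5/264.0) = 0.93, 3.4%
- 0.2/0.9: √(387.5/176.3) = 1.48, 18.6%

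*CST*, correlations 0.1 and 0.6:
- s = (22500 + 5×6400)/6 = 9083; c = (5×1200 + 10×3840)/15 = 2960
- compound symmetry 2(9083 − 2960) = 12247; true 22500 + 6400 − 2400 = 26500
- r = √(26500/12247) = 1.47; type I error **18.3%**

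*Equal SDs*, correlations 0.4/0.8: c = (5×0.4 + 10×0.8)/15 = 0.667 of the variance, so r = √(1.2/0.667) = 1.34 and type I error is 14.4%. Unequal correlation alone is enough.

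**3. Fallback, plain arm difference at month 29.** Here r = √(V29/s).
- BCVA: √(353.44/313.62) = 1.06, type I error 6.5% (too narrow)
- CST: √(6400/9083) = 0.84, type I error 2.0% (too wide)

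**4. Simulation.** With the inputs of step 2 (55 per arm, 6,000 runs), rejection for the interaction was 0.120 (BCVA) and 0.182 (CST) under compound symmetry, and 0.052 for both with the unstructured model. A second simulation (46 per arm, 10,000 runs) used six other assumed covariance patterns, one of them truly compound symmetric. It gave 0.053 to 0.183 under compound symmetry and 0.051 to 0.055 unstructured.

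**The case against.** **The random effect may be loose wording.** It could simply mean that visit is the repeated effect within patient. On that reading there are 21 parameters, all identified, and no redundancy. This is possible, but the text lists the random effect among the model terms and specifies the residual structure separately, so it needs to be settled.

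**A reader might infer that non-convergence is certain.** It is not. Redundancy makes a failure more likely, but some software will still return a fit, and the contrast is then unaffected.

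**A reader might infer that compound symmetry always gives intervals that are too narrow.** The protocol does not support that. The direction depends on a reference visit it does not name. The interaction against baseline is the natural reading, since baseline is one of the six time points, but even there the BCVA grid includes a conservative corner (3.4%). For a plain month-29 difference the CST interval comes out too wide. If the response were individual change over the five later visits only, the covariances assumed in step 2 would satisfy compound symmetry exactly and there would be no error.

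**The BCVA SDs are not this trial's.** They come from a 22-patient before/after-laser cohort in which 17 had earlier steroid or anti-VEGF injections. CoRaLa II excludes such patients (exclusion criteria 8 and 9). This objection stands: the SDs illustrate and do not predict. The equal-SD result of 14.4% does not depend on them.

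**Conclusion.** The point holds as a moderate one. As written, the random effect is redundant next to the unstructured residual, and the text should say what it means. The single fallback imposes equal variances and correlations that the design makes doubtful, and it relies on model-based standard errors with no protection.

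For the month-29-versus-baseline interaction, the 5% test runs at about 12% for BCVA (3% to 19% over the grid) and about 18% for CST. This rests on complete data, the assumed SDs, and a lower correlation with baseline than among later visits. For a plain month-29 difference the same assumptions give 6.5% and 2%. None of these sizes can be claimed for this population.

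The error arises only if the unstructured fit fails. It concerns BCVA and CST alone; the confirmatory Cox analysis of the primary endpoint is untouched.

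**What to change.** In section 9.5.2, and in the SAP to match:
1. Delete the patient-specific visit random effect, or state that visit is the repeated, residual-side effect within patient.
2. Keep the unstructured residual covariance with REML.
3. State the response and the month-29 contrast, including its reference visit. If the response is individual change from baseline, remove the baseline record from the modelled visits.
4. Replace the compound-symmetry fallback by heterogeneous structures in a fixed order, for example heterogeneous Toeplitz, then heterogeneous AR(1), with empirical sandwich standard errors for any structured fallback.

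The degrees-of-freedom method can be left to the SAP. The cost is a few sentences; no visit, data item or sample size changes.

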9.6 Statistical Monitoring

Regular monitoring visits and timely supervision of study documentation including a regular query management will be performed to ensure data quality and completeness acc. to ZKS Leipzig SOPs; it will be based on a risk-adapted monitoring concept.

The on-site monitoring (see chapter 13.2) will be supported by a regular central (statistical) off-site monitoring. The objectives are

- to detect safety relevant signals as soon as possible
- to detect non-compliance and relevant protocol violations and to prevent their future occurrence by prompt reaction

Central statistical monitoring will start 10 months after inclusion of the first patient in front of the analyses for 1st annual safety report if statistically sufficient numbers of patients were already included to enable statistical statements. Findings will be queried for clarification with the centres.

Non-compliance and/or PVs identified will be discussed at the ZKS Leipzig study team, with the coordinating investigator and with the respective centre(s).

The risk factors defined by the risk analyses during trial planning and implementation will be supervised during trial implementation at regular intervals.

For example, activities of central monitoring may refer to:

- data quality (completeness, timely documentation, consistency, ...)
- recruitment rate and screening-failures (overall, per site and between-sites

- comparisons)
- incidence of AEs/SAEs (overall, per site and between-sites comparisons)
- surveillance and evaluation of drop-outs (reasons and frequencies; overall, per site and between-sites comparisons)
- surveillance and evaluation of protocol violations (reasons and frequencies; overall, per site and between-sites comparisons)

9.7 Final Analysis

Final analysis will be performed when the data of all enrolled patients have been collected, all DM procedures have been finalised and the database has been cleaned for analysis.

In case of a premature termination of the whole trial (due to organisational, financial or other reasons) a limited analysis of the data available up to then may be suitable if at least 2 thirds of sample size finished the trial. A power analysis may add information regarding the study results and for future trials.

The decision on its extent and timely priority will be made in common voting of the ZKS Leipzig und the coordinating investigator.

No scheduled interim analysis is planned.

10 ETHICAL, LEGAL AND ADMINISTRATIVE ASPECTS

10.1 GCP-Statement

All persons participating in the conduct of the trial (sponsor, authorised representative of the sponsor, investigators, etc.) commit themselves to observe the Declaration of Helsinki of the WMA (in its current version), as well as all pertinent national laws and the ICH guideline for Good Clinical Practice (GCP) ICH E6(R2) ([EMA/CHMP/ICH/135/1995](#)) issued in June 2017.

10.2 Initial Submission

10.2.1 Submission to the Ethics Committee and Federal Authority

Prior to submitting the trial related documents to the leading (and involved) ethics committee(s) and the responsible federal authority, the sponsor must enter the trial information into the European database for clinical trials (EudraCT).

Afterwards, the protocol and all other associated documents according to GCP-V §7 will be submitted to the leading ethics committee for approval. Parallel to the submission to the leading ethics committee (EC), each participating EC is informed of the submission and also receives a copy of the documents including those of the trial sites, which they have to approve. At the same time the study documents will be submitted to the responsible federal authority (PEI) according to the requirements of GCP-V §7.

The trial can start only after obtaining a positive review by the leading ethics committee and approval from the responsible federal authority. The written approval of the EC must be filed in the trial master file (TMF). Additionally, every participating centre must receive a copy of these documents to be filed in the investigator site file (ISF).

10.3 Protocol Amendments

Changes to an approved trial protocol have to be submitted to EC and CA and positively appraised before implementation of the changes, if the changes are such that they may affect the subjects' safety, e.g.:

- that they may affect the subjects' safety, (e. g. fundamental changes to the therapeutic procedures),
- result in further data collection that requires changes to the patient information and/or informed consent form,
- affect the interpretation of the scientific documents upon which the trial is based or the significance of the results of the trial,
- that they significantly affect the leadership or conduct of the trial.

Changes to the protocol may only be performed by the co-ordinating investigator in co-operation with the biometrician and/or DSMB.

After approval of the trial changes, all participating trial sites have to be informed about the changes in writing and supplied with potentially changed documents.

The whole process has to be documented in the Trial Master File (TMF).

11 DOCUMENTATION

11.1 General information and Access Rights

The Case report Form (CRF) in the context of a database for electronic data capture only will be designed by the ZKS Leipzig in cooperation with the Coordinating Investigator and provided as electronic form (eCRF). In order to facilitate the documentation as per protocol in case of malfunction of the electronic system or any of its components, a paper version of the CRF will be provided in the ISF (investigator site file). The content of this paper version will be transferred to the eCRF as soon as the electronic system is available again.

Special CRF forms will be provided as paper CRF:

- **SAE-forms**, because these have to be sent to the ZKS Leipzig in a printable version for submission to the relevant authorities

An eCRF will be provided for each patient. The patient will be identified as per Patient-ID only. The eCRF must be filled in shortly after each trial visit according to ICH Guideline E6 chapter 4.9.1 and to enable central monitoring of the trial data.

Access to the data base will be limited to authorised staff only. Authorisation is granted by the site's investigator using the trial specific staff signature and delegation log. Based on the staff signature and delegation log access to the eCRF will be granted by the responsible staff at the ZKS Leipzig.

Authorised staff members on site will be able to enter and update data as well as finalise data by electronic signature during the conduct of the trial according to a trial specific concept for documentation. This concept is based on the internal Standard Operating Procedures implemented by the ZKS Leipzig and follows the ICH Guideline E6. All entries and data changes will be tracked automatically including date, time and person who entered/changed information (audit trail). Major correction(s) or major missing data have to be explained.

11.2 Patient File and Source Data

All information required by the protocol and therefore collected during the clinical trial must be recorded by the Investigator or an authorised member of the trial team as source data in the source documentation for the trial (e. g. patient file).

Source data according to ICH Guideline E6 are defined as any information in original records and/or certified copies of original records of clinical findings, observations, or other activities in a clinical trial necessary for the reconstruction and evaluation of the trial. Source data are contained in source documents.

The Source Data Agreement is defining source data and their location for respective CRF entries. It will be filled in at the initiation visit, signed by the investigator or deputy investigator and filed in the trial master file.

In order to confirm the completeness, accuracy and consistency of the data with the data in the source documents the investigator or deputy investigator has to electronically sign each patient's CRF after his individual end of trial participation.

11.3 Data Management

For creation of the trial database the EDC tool secuTrial®, developed and distributed by interActive Systems GmbH (iAS), will be used. The database will be validated according to the Standard Operating Procedures (SOPs) of the ZKS Leipzig prior to data capture.

The information entered into the eCRF by the investigator or an authorised member of the trial team is systematically checked for completeness, consistency and plausibility by routines implemented in CDMS such that discrepancies can be dealt with at data entry. Errors and Warnings are listed in a validation report and can be resolved at any time during entry process. On completion of the data entry the site staff flags the eCRF-pages as 'data entry completed' (DEC).

During on-site monitoring or central/statistical monitoring, the monitor or the data manager at the Clinical Trial Centre may create a manual query for discrepancies that are identified after DEC. All eCRF-pages with queries are marked in the system and a report with all queries listed is available. The site staff is responsible for data correction and can resolve queries directly in the eCRF-page.

The ZKS Leipzig will supervise and support the solution of queries and will close all correctly resolved queries. In case a query cannot be solved, the data management staff may close the query in agreement with the trial biometrician.

During the whole course of the trial, a backup of the data is made on a daily basis according to the backup policies of the ZKS Leipzig. Unauthorised access to patient data is prevented by the access concept of the trial database which is based on a strict hierarchy and role concept. Any change of data (e.g. when data is changed in the database during query management) is recorded automatically via audit trail within the database.

At the end of the trial, once the database has been declared complete and accurate, the database will be locked. Thereafter, any changes to the database are possible only by joint written agreement between sponsor/sponsors authorised representative/coordinating investigator, biometrician and data manager.

11.4 Archiving

All relevant trial documentation (Trial Master File), the electronically stored data, the original CRFs and the final report will be stored for at least 10 years at the coordinating investigator / sponsor after the trial's completion.

At the investigating sites, the investigators' files, patient identification lists, signed written consent forms, copies of all CRFs and the patients' files will be stored for at least 10 years after the trial's completion. If local rules or other legal requirements (e.g. Strahlenschutzverordnung, Röntgenverordnung) require longer periods of archiving, then these are to be met.

12 Reference evaluations

A **Central Reading Center** (CoRaLa II Reading Center) of experienced ophthalmologists will review coloured fundus images and FA images from all patients. Two independent graders will independently define the areas of capillary non-perfusion as a target for the laser photocoagulation, which will be performed in each study site according to the standardized protocol. In the case of divergent opinions between two grades a third one will perform an additional independent grading. A consented plan will be transferred to the patient's site and recommend on details of the laser treatment, according to the imaging protocol.

13 Supervision of the clinical trial

